4.2.11. Blood pressure and dialysis hypotension. Maintenance of blood pressure on dialysis can be a challenge for some patients, particularly those with large intra-dialytic fluid gains, and is associated with poor outcomes.⁶⁹ A prior study of EMS during hemodialysis found that EMS produced a statistically significant increase in BP and fewer hypotensive episodes compared to no EMS.²⁹ For the first EMS treatment in each patient we will directly record BP and pulse at 15-minute intervals before, during and after treatment with EMS. Thereafter, we will collect the BP and pulse data that is recorded (approximately every 15-30 minutes) as standard of care for every hemodialysis session. We will compare the average hemodialysis BP and pulse during the 4-week “care optimization” phase to that obtained during the EMS treatment and the 4-week post-EMS treatment phases to determine if EMS was associated with any change in BP or pulse. We will also analyze the frequency of dialysis sessions with a hypotensive episode (defined as SBP<90 mmHg or need for IV saline for hypotensive symptoms) during EMS compared to non-EMS treatment.

4.2.12. Muscle gene expression. Gene expression profiling of mRNA extracted from a skeletal muscle biopsy will be performed to give insight into the biological pathways activated by EMS both acutely and with chronic training in hemodialysis patients. Patients will be allowed to opt out of any of the muscle biopsy samples and still participate in the rest of the study. For these studies a muscle biopsy will be obtained as previously described⁷⁰ from the vastus lateralis muscle prior to the first EMS

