8. Statistical analysis/Power calculations.

This is a pilot feasibility and preliminary efficacy study to determine whether EMS can be delivered to this population and to assess the magnitude of the change and variability in the primary and secondary outcome measures. Data derived from this study will allow planning of a larger randomized controlled study. We plan to recruit up to 15 patients into the trial and complete the trial within 1 year. There will be 5 measurements of the primary and most of the secondary outcome variables in each patient. These will be performed at enrollment, after 4 weeks of "dialysis care

optimization" before starting the EMS intervention, then at 8 and 16 weeks after initiation of the EMS intervention and finally 4 weeks after stopping EMS. The DXA scan, measurement of peak VO₂ will only be performed three times (before starting EMS and then again at 8 and 16 weeks of EMS training). The optional muscle biopsy for gene expression analysis will be performed up to 4 times in patients who agree to this analysis (before and after the first EMS treatment, at 8 and 16 weeks of EMS training). Summary statistics will be used to describe and analyze the data. Changes over time in the outcome variables will be analyzed using the Friedman analysis of variance by ranks to determine if there was a statistically significant effect of EMS. A P<0.05 will be considered statistically significant. Regression analysis will be used to determine if the change in HOMA-IR or LAR is correlated with the magnitude of the observed exercise training effect (i.e. the increase in peak VO₂ or quadriceps muscle strength at 4 months) or maximum intensity of EMS stimulation used during training.

Based on an estimated baseline mean (\pm SD) HOMA-IR score of 4.8 (\pm 1.7) mg/dl· μ U/ml, a sample size of 15 patients will provide 80% power to detect a 28% decrease in the HOMA-IR score (by a paired t-test analysis) at the P=0.05 level. This decrease in HOMA-IR score would be predicted to be associated with a clinically significant reduction in mortality.³³

9. Selected methods

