9.8. Gene expression profiling. Gene expression profiling is done using the Human Exon 1.0 ST arrays (Affymetrix, Inc) which measures >17,000 different mRNA transcripts with about 4 probes per exon and 40 probes per gene. This recognizes both the gene being expressed and differences in alternative splice variants of that gene. To perform gene expression analysis total RNA must be extracted, converted to cDNA, the cDNA amplified, sense target cDNA prepared and then fragmented and labeled for detection prior to applying to the gene expression arrays.

As previously described⁷⁰, total RNA is extracted using TRIzol solution (Invitrogen) according to manufacturer's instruction. Microarray hybridization will be performed at the University of Iowa DNA facility.⁷⁰ Briefly, 50 ng total RNA is converted by Single Primer Isothermal Amplification (SPIA) to cDNA using the whole transcriptome (WT)-Ovation Pico RNA Amplification System (NuGEN Technologies, San Carlos, California). The amplified cDNA product is purified through a Qiagen MinElute Reaction Cleanup Column (Qiagen). A 4- μ g quantity of amplified cDNA was used to generate sense target (ST)-cDNA using the WT-Ovation Exon Module (NuGEN Technologies), and again cleaned up with the Qiagen column. A 5- μ g quantity of this product is fragmented (50-100 bases) and biotin labeled using the NuGEN FL-Ovation cDNA Biotin Module (NuGEN Technologies) prior to use for gene expression profiling.

For gene expression analysis the resulting biotin-labeled cDNA is mixed with eukaryotic hybridization buffer (Affymetrix, Inc., Santa Clara, California), placed onto Human Exon 1.0 ST arrays and incubated at 45°C for 18 h with 60-rpm rotation in a GeneChip hybridization oven (Model 640; Affymetrix). After hybridization, the arrays are washed, stained with streptavidin-phycoerythrin (Molecular Probes, Inc., Eugene, Oregon), and signal amplified with anti-streptavidin antibody (Vector

Laboratories, Inc., Burlingame, California) using a fluidics station (Model 450; Affymetrix). Arrays are scanned (Model 3000 7G scanner; Affymetrix) and data collected using the using GeneChip operating software (GCOS), version 1.4.

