In Affymetrix Human Exon 1.0 ST arrays, the log2 hybridization signal reflects the mean signal intensity of all exon probes specific for an individual mRNA, and is proportional to the level of that mRNA. We will perform two main comparisons: 1) the effect of acute exercise comparing the gene expression levels 4 hours after the first EMS training to baseline before training and 2) the effect of chronic EMS training (8 and 16 weeks) compared to the Pre-EMS training sample. We will restrict the analysis to mRNA's that have a mean log2 hybridization signal of >5 in either the pre-EMS sample or the 8 or 16 week EMS treatment conditions. We will use paired t-tests to determine which of the remaining mRNA's are present at a significantly different level (adjusting for the false discovery rate inherent in multiple testing) in the EMS treatment compared to the baseline sample. The list of differentially expressed genes will be examined for important biological pathways relating to muscle glucose metabolism and insulin response, mitochondrial biogenesis and function, muscle phenotype, growth and energy metabolism, oxidant stress and inflammation. We will also use bioinformatics tools such as Onto-Express to help translate the list of differentially expressed genes into functional categories such as biological process or cellular role based on the annotation using Gene Ontology terms. All microarray data will be deposited in the GEO database.

10. References

1. U.S. Renal Data System, *USRDS 2012 Annual Data report: Atlas of End-Stage Renal Disease in the United States*, National Institutes of Health, National Institute of Diabetes and Digestive and Kidney Diseases, Bethesda, MD, . 2012.
2. Carrero JJ, de Jager DJ, Verduijn M, et al. Cardiovascular and noncardiovascular mortality among men and women starting dialysis. *Clin J Am Soc Nephrol*. Jul 2011;6(7):1722-1730.
5. Johansen KL. Exercise in the end-stage renal disease population. *J Am Soc Nephrol*. Jun 2007;18(6):1845-1854.

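### Gene expression (section 9.8): ordinary gene-wise paired t-tests in at most 15 patients with optional biopsies are valid but inefficient; a variance-moderated paired t-test would find more of the large changes at the same false discovery rate

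*Combined protocol and SAP*

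**What the plan says.** Section 9.8 (Gene expression profiling) describes an array "which measures >17,000 different mRNA transcripts". That figure is the content of the array. A filter comes before any test: "We will restrict the analysis to mRNA's that have a mean log2 hybridization signal of >5" in the pre-EMS, 8-week or 16-week condition. The number of mRNAs expected to pass is not given.

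The test is then specified: "We will use paired t-tests to determine which of the remaining" mRNAs differ from baseline, with the qualification "adjusting for the false discovery rate inherent in multiple testing". The FDR procedure and level are not stated, and no pooling of variance information across mRNAs is mentioned. The comparisons are the acute sample (4 hours after the first session) and the 8- and 16-week samples, each against pre-EMS. The list of differentially expressed genes then feeds the pathway and Gene Ontology work.

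On numbers, section 8 says "We plan to recruit up to 15 patients into the trial". Section 9.7 makes biopsies optional, and section 4.2.12 adds "Patients will be allowed to opt out of any of the muscle biopsy samples" while remaining in the study. No biopsy uptake, gene-level SD, effect size or power is given for this outcome.

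**The concern.** With n pairs, an ordinary paired t-test estimates each mRNA's variance on n − 1 degrees of freedom: 5 df with 6 pairs, 7 df with 8. Such variances are unstable, and the t cut-off needed to survive an FDR adjustment over thousands of tests is very high. Many real changes then miss the cut-off even though the neighbouring mRNAs on the same arrays hold usable information about typical variability.

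At stake is the length of the gene list. Muscle gene expression is a named secondary outcome, the list is the input to the pathway analysis, and patients undergo an invasive procedure to supply it.

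**Working it through.** **The plan's own figure.** There is none for gene expression. The only power statement, in section 8, concerns HOMA-IR. With a change of 0.28 × 4.8 = 1.344, the SD of differences taken as 1.7, n = 15 and two-sided 5%, the noncentral-t power is 81.2%, so the stated 80% reproduces. It has no bearing on the arrays.

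**Inputs from the documents.** At most 15 patients; any biopsy optional; an array of more than 17,000 transcripts with a log2 > 5 filter; gene-wise paired t-test; FDR adjustment.

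**Inputs assumed.** 10,000 mRNAs after filtering; 5% truly changed; change 0.6 log2; typical SD of paired log2 differences s₀ = 0.35; gene variances scattered around s₀² with prior df d₀ = 4; independent genes; Benjamini-Hochberg at 5%.

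**The two tests.** For mean difference m, sample variance s² and n pairs:
- ordinary: t = m / √(s²/n), on n − 1 df;
- moderated: replace s² by (d₀s₀² + (n − 1)s²) / (d₀ + n − 1), on d₀ + n − 1 df, with d₀ and s₀ estimated from all mRNAs together.

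**Why the number of pairs matters.** Suppose 200 of 10,000 mRNAs are declared. The Benjamini-Hochberg cut-off is then p = 0.05 × 200 / 10,000 = 0.001.
- 6 pairs: a typical changed mRNA has an expected t of about 0.6 / (0.35/√6) = 4.2. The two-sided cut-off is 6.87 on 5 df, but 4.78 on 4 + 5 = 9 df.
- 15 pairs: the expected t is about 0.6 / (0.35/√15) = 6.6. The cut-offs are 4.14 on 14 df and 3.92 on 18 df, so there is little left to gain.

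**Simulated share of true changes found** (0.6 log2, SD 0.35, d₀ = 4):

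| Pairs | Ordinary | Moderated |
|---|---|---|
| 6 | 4% | 30% |
| 8 | 39% | 62% |
| 10 | 63% | 75% |
| 15 | 84% | 89% |

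Realised FDR was about 5% for both tests. Repeat runs differed by a few points at most (6 pairs: 3–4% against 26–30%). With 4 or 5 pairs neither test found anything appreciable in this setting.

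**Sensitivity.**
- *Effect of about 1 SD.* At 0.35 log2 with SD 0.35, the shares (ordinary against moderated) are 0% against 0% with 6 pairs, 1.1% against 0.1% with 8, 7% against 5% with 10, 23% against 25% with 12, and 40% against 45% with 15. The advantage is absent or slightly negative up to 10 pairs.
- *Similarity of variances.* At 1.0 log2 with SD 0.5 and 6 pairs: 14% against 33% (d₀ = 2), 15% against 58% (d₀ = 4), 12% against 83% (d₀ = 10).
- *Number of mRNAs.* At 1.0 log2, SD 0.5, d₀ = 4 and 8 pairs, using 5,000, 10,000 or 17,000 mRNAs gives 55–57% against 76–78%. The unstated filter yield hardly matters.
- *FDR 10%.* In the same setting: 67% against 83% with 8 pairs, 92% against 95% with 15.

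**Pooling all time points.** One patient-blocked moderated model over three complete time points, with equal residual variance, found still more in the main setting: 51% with 6 pairs and 69% with 8. It depends on that equality. Suppose four samples per patient and twice the SD at the acute sample. The pooled variance averages (4 + 1 + 1 + 1)/4 = 1.75 units, so every contrast is given 2 × 1.75 = 3.5. The true values are 4 + 1 = 5 for acute against pre-EMS and 1 + 1 = 2 for week 8 against pre-EMS. In null simulations with 8 patients, rejection at nominal 5% was 10.1–10.3% for acute and 1.3% for week 8. With an SD ratio of 1.5 it was 7.7% and 2.8%. The ordinary paired t held about 5%, and the moderated paired t applied to each contrast separately held 4.9–5.1%.

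**The case against.** The planned analysis is a paired, FDR-adjusted, accepted method for an optional, hypothesis-generating outcome in a pilot. It controls its error rate and is robust to unequal variance across time points. Every gene-level input above is assumed, and the simulated variances follow the moderated test's own model. The gain is about 5 points with 15 pairs, and the documents do not show that uptake will be lower. All of this stands, and it limits the point to efficiency.

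A reader might also infer several stronger things that the documents do not support:
- *That more than 17,000 transcripts will be tested.* That is the array content; only those passing the filter are tested.
- *That only a few patients will accept biopsies.* Uptake is not stated. What is known is a ceiling of 15 and a right to decline each sample.
- *That the gene lists would be biased or less reproducible.* Realised FDR was about 5% for both tests.
- *That the loss is permanent.* Section 9.8 commits to depositing all microarray data publicly, so a moderated reanalysis remains possible.
- *That one pooled model over all biopsies is a free upgrade.* It is stronger under equal variances but misstates error rates when one time point is more variable, and a sample taken 4 hours after stimulation could plausibly be so.

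None of this removes the narrower point. Moderating each contrast separately keeps the error rate and finds more of the large changes when pairs are few.

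**Conclusion.** The point holds as an efficiency improvement. With roughly 6 to 10 pairs and changes of about 0.6/0.35 = 1.7 SD, the moderated paired test finds 12 to 26 percentage points more of the true changes (75 − 63 = 12 with 10 pairs; 30 − 4 = 26 with 6). With 15 pairs the gain is 89 − 84 = 5 points. For changes near 1 SD with 10 or fewer pairs there is no gain and possibly a loss of 1 to 2 points. With 4 or 5 pairs the result depends on the assumptions: at 1.0 log2 and SD 0.5, 5 pairs gave 0.6% against 27% with d₀ = 4 but 0.8% against 0% with d₀ = 2.

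These sizes rest on assumed effect sizes, SDs and similarity of variances, none of which the documents give. The direction for large changes with 6 to 10 pairs held at each prior df tried (2, 4 and 10).

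**What to change.** In section 9.8, replace the paired t-tests with empirical-Bayes moderated paired t-tests applied to the within-patient log2 differences of each contrast (each post-EMS sample against pre-EMS). Name the Benjamini-Hochberg procedure and a level, such as 5%. Keep a single patient-blocked model over all time points as a sensitivity analysis, or use it only if residual variances are shown to be similar across times.

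The cost is a sentence or two and standard free software; no new samples, arrays or visits are needed. The small downside is the assumption of a common prior for the gene variances and a possible loss of a few percentage points of detection for small effects.

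The same edit should make clear which contrasts exist. Sections 8 and 9.8 count a biopsy after the first EMS session, while section 9.7 lists three time points and section 5.3 lists only a pre-EMS biopsy. These passages must be reconciled.

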treatment and after 8 and 16 weeks of EMS training to determine the chronic effect of EMS training on muscle gene expression. Gene expression analysis will be done using Affymetrix Human Exon 1.0 ST arrays as previously described.⁷⁰ We will first examine specific genes that are highly overexpressed or under-expressed after acute and chronic exercise compared to the baseline (pre-EMS). We will also look for biological pathways activated or suppressed by acute and chronic exercise specifically looking at pathways relating to muscle glucose metabolism and insulin response, mitochondrial biogenesis and function, muscle phenotype, growth and energy metabolism, oxidant stress and inflammation. A future goal of this research is to compare the gene expression response to EMS in this study with that seen in patients with normal renal function and varying levels of CKD to see if the gene response profile is qualitatively different in patients with varying levels of kidney function. We are also interested how the gene expression profiles seen with EMS compare to that seen with traditional volitional aerobic exercise to determine if EMS activates different genes or biological pathways than volitional exercise.

5. Visits & Assessments.

Patients will be identified from the population of patients on regular maintenance hemodialysis at one of the University of Iowa dialysis units. Potential subjects will be approached at a dialysis visit and informed of the study.

5.1. Visit 1. If they indicate an interest in participating we will proceed with obtaining written informed consent and confirm that they meet all the inclusion criteria and none of the exclusion criteria.

- Obtain informed consent to participate and consent to access additional appropriate medical records
- Review inclusion and exclusion criteria

Baseline data collection (Day -35 to -28). Performed at dialysis unit or CRU as appropriate. Up to 4 hours time.

- Record demographics and baseline disease characteristics
- Record past medical history and current review of symptoms
- Record current dialysis orders
- Record episodes of dialysis hypotension (SBP<90 or symptoms needing saline, last 6 HD sessions)
- Record baseline exercise status (minutes of exercise per week)
- Record concomitant medications
- Malnutrition-inflammation (MIS) assessment
- Kidney Disease Quality of Life-36 (KDQOL-36) assessment
- Patient Health Questionnaire-9 (PHQ-9)
- Record sitting blood pressure and pulse

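### Section 9.8 reads pathway activation from a gene-level list with no pathway-level comparison to chance, so overlap is weak evidence, especially for long lists or broad groups

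*Combined protocol and SAP*

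**What the plan says.** Section 9.8 describes arrays "which measures >17,000 different mRNA transcripts with about 4 probes per exon and 40 probes per gene". Analysis is limited to mRNAs with a "mean log2 hybridization signal of >5 in either the pre-EMS sample or the 8 or 16 week EMS treatment conditions". These are compared by paired t-tests, "adjusting for the false discovery rate inherent in multiple testing"; the false-discovery level is not stated.

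Two steps then lead from genes to pathways:

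- Inspection: "The list of differentially expressed genes will be examined for important biological pathways relating to muscle glucose metabolism and insulin response", and also "mitochondrial biogenesis and function, muscle phenotype, growth and energy metabolism, oxidant stress and inflammation". That is five or six broad groups, depending on how the phrase is split. No gene-set source or membership is given.
- Classification: "We will also use bioinformatics tools such as Onto-Express to help translate the list of differentially expressed genes into functional categories", using Gene Ontology annotation.

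Section 4.2.12 gives the purpose: "We will also look for biological pathways activated or suppressed by acute and chronic exercise". It also names later interests, namely how the expression response compares with that at other levels of kidney function and with volitional exercise. Section 8 adds nothing on pathways.

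**The concern.** The inference sought is about pathways, but the only stated error control is about single genes. False-discovery adjustment limits the share of listed genes that did not change. It says nothing about whether the genes that did change are concentrated in one pathway. A list made up wholly of real changes will contain members of broad categories simply because those categories hold many of the genes expressed in muscle. Without an expected count, a pathway that responds to EMS cannot be told from one that is merely well represented.

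A second issue arises if a category test is run later. Only mRNAs above the signal filter can reach the list, so a test that takes the whole array as its reference compares the list with genes that never had a chance of being on it.

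At stake is the credibility of statements that named pathways were activated or suppressed, and of later comparisons that build on them.

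**Working it through.** The plan states no figure for the pathway step, so there is nothing to reproduce. The check asks how often a list with no pathway-specific content overlaps the named groups.

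**Inputs from the documents.** More than 17,000 transcripts on the array and the log2 >5 filter (section 9.8); five or six named groups (sections 4.2.12 and 9.8); at most 15 patients (section 8), with biopsies optional (sections 4.2.12 and 9.7).

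**Assumptions, not in the documents.** N = 10,000 mRNAs pass the filter; each group has m = 100 expressed genes; there are six groups, treated as independent; the list of L genes is a random draw from the N.

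**Step 1: overlap by chance.** Expected members of one group on the list = L × m / N. The chance of at least one member is hypergeometric:

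P1 = 1 − C(N − m, L) / C(N, L)

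At least one of six groups: 1 − (1 − P1)^6. All six: P1^6.

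| List length L | Expected per group | P1 | At least one of six | All six |
|---|---|---|---|---|
| 20 | 0.2 | 0.18 | 70% | <0.1% |
| 50 | 0.5 | 0.396 | 95.1% | 0.4% |
| 100 | 1.0 | 0.636 | 99.8% | 6.6% |
| 200 | 2.0 | 0.869 | >99.9% | 43% |
| 500 | 5.0 | 0.994 | >99.9% | 97% |

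For example, at L = 100: 1 − (1 − 0.636)^6 = 0.998 and 0.636^6 = 0.066.

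**Step 2: sensitivity.**

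- Groups of 200 genes: P1 = 0.637, 0.869, 0.983 and 1.000 for lists of 50, 100, 200 and 500.
- N from 8,000 to 12,000 (m = 100, L = 200): P1 from 0.922 to 0.815.
- All 17,000 transcripts as N, with five groups of 200: a list of 100 touches at least one group in 99.7% and all five in 16%; a list of 20 touches at least one in 69% and all five in under 0.1%.
- Very short lists and narrow groups (N = 17,000, L = 5, m = 50): at least one of five groups in 7%.

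**Step 3: reference set, if a category test were run.** Take the smallest count with one-sided p ≤ 0.05 when the reference is 17,000, then find how often a random list from the 10,000 filter-passing mRNAs reaches it.

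| Pathway size, list length | Attained level, 17,000 reference | All pathway genes pass filter | 90% pass |
|---|---|---|---|
| 100, 200 | 3.0% | 14% | 11% |
| 100, 500 | 2.8% | 23% | 16% |
| 200, 200 | 3.1% | 21% | 15% |
| 200, 500 | 3.5% | 42% | 29% |

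If pathway genes pass at the array-wide rate (10,000/17,000 = 59%), the rate returns to about 3% in all four cases. With lists of 50 and every pathway gene expressed it is 8% to 9%. The inflation thus comes entirely from pathway genes passing the filter more often than other genes.

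**Step 4: what a test would ask for.** With N = 10,000, m = 100 and a Bonferroni threshold of 0.05/6 = 0.0083, a list of 100 (1 expected) needs at least 5 members (tail p = 0.0032), and a list of 500 (5 expected) needs at least 12 (p = 0.0041). These counts differ greatly from the single member behind Step 1.

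**The case against.** The strongest reply is that the plan is silent rather than wrong. It nowhere says that one listed gene makes a pathway activated, so the Step 1 figures describe a rule the plan does not contain. Onto-Express is said only to "help translate the list of differentially expressed genes into functional categories such as biological process or cellular role"; whether its expected counts or p-values would be used is neither confirmed nor excluded. This stands, and the Step 1 figures should be read as showing how little overlap alone can prove. It does not remove the gap: for a stated aim of finding activated or suppressed pathways, the text supplies no criterion at all.

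A reader might infer that almost any gene list would show every hoped-for pathway. The documents do not support that. The high percentages for moderate lists refer to at least one group; all six are touched in only 0.4% of lists of 50 and 6.6% of lists of 100. With at most 15 patients, optional biopsies and false-discovery adjustment, a short or empty list is quite possible.

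A reader might also infer that false-positive rates of 14% to 42% apply to this trial. They do not follow: no category test is stated, no reference set is named, and the inflation vanishes if pathway genes pass the filter at the array-wide rate.

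Finally, this is an optional, exploratory part of a pilot, and all array data are to be deposited publicly, so others can test gene sets later. That limits the stakes but does not support a claim of activation in the trial's own report.

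**Conclusion.** The point holds in limited form. Sections 9.8 and 4.2.12 aim at pathway conclusions but state no pathway-level comparison with chance, and gene-level false-discovery control does not provide one. Overlap with a broad named group is therefore weak evidence. The weakness grows with list length and group breadth: under the assumptions above, some group is touched in over 99% of unrelated lists of 100, and all six in about 97% of unrelated lists of 500. Short lists are much less affected, and an empty list leaves nothing to interpret. A whole-array reference could add false positives, but only to the extent that pathway genes pass the filter more often than other genes.

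The number of mRNAs passing the filter, the group sizes, the list lengths and independence between groups are all assumptions. It would go too far to call a pathway finding close to guaranteed. The primary outcome is unaffected. The change is still worth making, because a better-defined method is available at little cost.

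**What to change.** In section 9.8:

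1. Define the gene set for each named pathway (for example by Gene Ontology terms) before the array data are analysed.
2. Test each set with a standard gene-set method: over-representation, a rank-based test, or a correlation-adjusted competitive test on the paired differences, such as CAMERA. Any of these would do if named in advance.
3. Use as background only the mRNAs that pass the log2 >5 filter.
4. Control the false discovery rate across sets, at a stated level.
5. Call a pathway activated or suppressed only when its set passes and the direction of change is consistent.
6. Label the list inspection and the Onto-Express output as descriptive.

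The cost is a paragraph of analysis-plan wording and some standard software, with no new samples or arrays. The downside is that, with at most 15 patients and optional biopsies, fewer pathways will be declared.
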